10. SUPPORTING DOCUMENTATION AND OPERATIONAL CONSIDERATIONS

10.1. Regulatory, Ethical, and Study Oversight Considerations

10.1.1. Regulatory and Ethical Considerations

This study will be conducted in accordance with the protocol and with the following:

- Consensus ethical principles derived from international guidelines, including the Declaration of Helsinki and Council for International Organizations of Medical Sciences (CIOMS) International Ethical Guidelines
- Applicable ICH Good Clinical Practice (GCP) Guidelines
- Applicable laws and regulations

The protocol, protocol amendments, ICF, Investigator Brochure, and other relevant documents (e.g., advertisements) must be submitted to an IRB/IEC by the Investigator and reviewed and approved by the IRB/IEC before the study is initiated.

Any amendments to the protocol will require IRB/IEC approval before implementation of changes made to the study design, except for changes necessary to eliminate an immediate hazard to study participants.

The Investigator will be responsible for the following:

- Providing written summaries of the status of the study to the IRB/IEC annually or more frequently in accordance with the requirements, policies, and procedures established by the IRB/IEC
- Notifying the IRB/IEC of SAEs or other significant safety findings as required by IRB/IEC procedures
- Providing oversight of the conduct of the study at the site and adherence to requirements of 21 CFR, ICH guidelines, the IRB/IEC, European regulation 536/2014 for clinical studies (if applicable), and all other applicable local regulations

10.1.2. Financial Disclosure

Investigators and sub-Investigators will provide the Sponsor with sufficient, accurate financial information as requested to allow the Sponsor to submit complete and accurate financial certification or disclosure statements to the appropriate regulatory authorities. Investigators are responsible for providing information on financial interests during the course of the study and for 1 year after completion of the study.

10.1.3. Informed Consent Process

Each interested prospective participant (or legally authorized representative) will receive an informed consent document that contains study information and be given ample time to read the information and consider participation. The Investigator or his/her representative will explain the nature of the study and its risks and potential benefits to the prospective participant or his/her legally authorized representative and answer all questions regarding the study.

Prospective participants must be informed that the study involves research, their participation is voluntary, and that the choice not to participate or to discontinue the study at any time will involve no penalty or loss of benefits to which the individual is otherwise entitled. Consenting participants, or their legally authorized representatives, will be required to sign a statement of informed consent that meets the requirements of 21 CFR 50, local regulations, ICH guidelines, Health Insurance Portability and Accountability Act (HIPAA) requirements, where applicable, and the IRB/IEC or study center.

The medical record must include a statement that written informed consent was obtained before the participant was enrolled in the study, and the date the written consent was obtained. The authorized person obtaining the informed consent must also sign the ICF.

Participants must be re-consented to the most current version of the ICF(s) during their participation in the study.

A copy of the ICF(s) must be provided to the participant or the participant's legally authorized representative.

10.1.4. Data Protection

Participants will be assigned a unique identifier by the Sponsor. Any participant records or datasets that are transferred to the Sponsor will contain the identifier only; participant names or any information which would make the participant identifiable will not be transferred.

The participant must be informed that his/her personal study-related data will be used by the Sponsor in accordance with local data protection law. The level of disclosure must also be explained to the participants, who will be required to give consent for their data to be used as described in the informed consent

The participant must be informed that his/her medical records may be examined by Clinical Quality Assurance auditors or other authorized personnel appointed by the Sponsor, by appropriate IRB/IEC members, and by inspectors from regulatory authorities.

10.1.5. Committees Structure

10.1.5.1. Safety Review Committee

The SRC will comprise the PI and/or sub-Investigator, the Sponsor Medical Monitor, and the CRO Medical Monitor.

See [Section 9.5](#) for further details regarding the SRC.

10.1.5.2. Data Safety Monitoring Committee

The independent DSMC will comprise appropriately qualified clinicians who are not involved in the study. The DSMC will provide a comprehensive review of study safety and tolerability data on an ad hoc basis. Further operational details will be prespecified in the DSMC charter.

10.1.6. Dissemination of Clinical Study Data

Data collected during the study will be shared with Investigators whose proposed use of the data has been approved by an independent review committee. A tabular summary of study results will be posted to www.ClinicalTrials.gov within 1 year of study completion.

10.1.7. Data Quality Assurance

[REDACTED] will use an electronic data capture system to completely collect all medical data during this trial. ClinBase™ is a software tool designed similarly to an electronic medical record for the documentation of e.g., medical history, demographics, vital signs, and AEs. Unlike a system (which is relying on data from other sources like paper records and is setup just to digitize these data for transmission), ClinBase ensures quality assurance and enables comprehensive capture of all relevant medical information gathered during clinical studies. Through a system provided workflow that includes barcode scanning and interfaces to medical equipment, trial operations performance is controlled and captured in real time. Thus, the system provides 100% transparency for monitors and is at any time accessible to the Investigators and clinical personnel for all medical documentation processes.

ClinBase meets ICH GCP requirements as data are attributable, legible, contemporaneous, original, accurate, and complete (ALCOA-C). The system is fully Code of Federal Regulations (CFR) Title 21 Part 11 compliant.

The Investigator will ensure the accuracy, completeness and timeliness of the data reported to the Sponsor. System supported data collection processes and procedures are validated to ensure completeness, accuracy, reliability, and consistency. A complete audit trail is maintained of all data changes. The Investigator or designee will cooperate with the Sponsor's representative(s) for the periodic review of trial documents to ensure the accuracy and completeness of the data capture system at each scheduled monitoring visit.

Electronic consistency checks (plausibility and completeness) will be used along with the Investigator review to identify any errors or inconsistencies in the data. Data clarification requests will be provided to the trial team by means of electronic or manual queries.

During the trial setup, adequate and accurate clinical procedure forms are used to generate medical records, digital ECGs, AE and concomitant medication reporting, raw data collection forms, etc., which are designed as protocol to record all observations and other pertinent data for each subject receiving trial medication. The only regularly used paper-based trial document is the ICF because it requires wet-ink signatures. The ICFs will be archived in paper form at the end of the trial. Should additional paper forms be used, the recorded data must be transferred into ClinBase accurately and within due time. In pre-stabilized intervals or at the end of the trial, data will be exported from ClinBase data management systems for further processing.

The Investigator will allow Sponsor representatives, contract designees, authorized regulatory authority inspectors and the IRB to have direct access to all electronic records pertaining to the trial.

All data should be recorded, handled, and stored in a way that allows its accurate reporting, interpretation, and verification.

Monitoring details describing strategy (e.g., risk-based initiatives in operations and quality such as Risk Management and Mitigation Strategies and Analytical Risk-Based Monitoring), methods, responsibilities, and requirements, including handling of noncompliance issues and monitoring techniques (central, remote, or on-site monitoring) are provided in the Monitoring Plan.

The Sponsor or designee is responsible for the data management of this study, including quality checking of the data.

The Sponsor assumes accountability for actions delegated to other individuals (e.g., CROs).

Study monitors will perform ongoing source data verification to confirm that data entered into the eCRF by authorized site personnel are accurate, complete, and verifiable from source documents; that the safety and rights of participants are being protected; and that the study is being conducted in accordance with the currently approved protocol and any other study agreements, ICH GCP, and all applicable regulatory requirements.

Records and documents, including signed ICFs, pertaining to the conduct of this study must be retained by the Investigator for 5 years after study completion unless local regulations or institutional policies require a longer retention period. No records may be destroyed during the retention period without the written approval of the Sponsor. No records may be transferred to another location or party without written notification to the Sponsor.

10.1.8. Study and Site Start and Closure

The study start date is the date on which the clinical study will be open for recruitment of participants.

The first act of recruitment is site activation and will be the study start date.

The Sponsor designee reserves the right to close the study site or terminate the study at any time for any reason at the sole discretion of the Sponsor. Study sites will be closed upon study completion. A study site is considered closed when all required documents and study supplies have been collected and a study-site closure visit has been performed.

The Investigator may initiate study-site closure at any time, provided there is reasonable cause and sufficient notice is given in advance of the intended termination.

Reasons for the early closure of a study site by the Sponsor or Investigator may include but are not limited to:

- Investigator noncompliance with the protocol, GCP, or regulatory requirements
- Unsatisfactory enrollment with respect to quantity or quality
- Incomplete data collection; inaccurate or knowingly false data submission
- The PI is no longer capable of performing the tasks of the PI, and no replacement can be found.
- The SRC determines that termination of the study is in the best interest of the research participants.
- The Sponsor, Investigator or IRB/IEC determines that continuation of the study will not serve any scientific purpose.

- Circumstances beyond the control of the Sponsor or Investigator make it unreasonable to require the study's continuation.
- A request to discontinue the study by a regulatory or health authority.

If the study is prematurely terminated or suspended, the Sponsor shall promptly inform the Investigators, the IECs/IRBs, the regulatory authorities, and any CRO(s) used in the study of the reason for termination or suspension, as specified by the applicable regulatory requirements. The Investigator shall promptly inform the participants and should assure appropriate participant therapy and/or follow-up. The complete set of stopping rules is detailed in [Section 7](#).

10.1.9. Publication Policy

Publication of a summary of the results of the study is permissible according to the Sponsor and is not inconsistent with the preceding affirmation. Scientific dissemination of the results of this study is encouraged. Any formal publication of data collected as a result of the study will be considered a joint publication by the Investigator and the appropriate personnel of the Sponsor or their designees. Authorship will be determined by mutual agreement and in line with International Committee of Medical Journal Editors authorship requirements.

No submission of a manuscript may be made until the results from the study site have been received and analyzed by Sponsor, or the study has been terminated at all centers. A separate, individual publication of the results of the study will be delayed until initial publication of the results of the multi-center study, or a decision not to publish is made. Please refer to clinical study agreement for further details.

For any publication or presentation, a manuscript of the paper or abstract must be received and approved by the Sponsor prior to outside submission. Whether or not there is a Sponsor author of the publications or presentations, a manuscript will be forwarded to the Sponsor for review and approval at least 30 days prior to submission of a journal publication, or at least 10 days prior to submission of an abstract.

Note: Any language relating to these issues appearing in the clinical study agreement will supersede that which is outlined in this section.

10.2. Clinical Laboratory Tests

[Table 6](#) summarizes the laboratory tests to be conducted. Full details for the testing are provided in the laboratory manual. Protocol-specific requirements for inclusion or exclusion of participants are detailed in [Section 5](#).

Additional tests may be performed during the study as determined necessary by the Investigator or required by local regulations.

Investigators must document their review of each laboratory safety report.

Laboratory/analyte results that could unblind the study will not be reported to investigative sites or other blinded personnel until the study has been unblinded.

Table 6: Protocol-Required Safety Laboratory Assessments

Laboratory Assessments	Parameters	
Hematology	Complete Blood Cell Count: red blood cells hemoglobin hematocrit platelets white blood cells	Complete Blood Cell Count with differential and RBC indices: red blood cells hemoglobin hematocrit platelets reticulocytes mean corpuscular volume (MCV) mean corpuscular hemoglobin (MCH) mean corpuscular hemoglobin concentration (MCHC) white blood cells: lymphocytes, abs and % monocytes, abs and % eosinophils, abs and % neutrophils, abs and % basophils, abs and %
Coagulation parameters	International normalized ratio (INR), prothrombin time (PT), partial thromboplastin time (PTT)	
Clinical chemistry	alanine transaminase (ALT) aspartate transaminase (AST) gamma-glutamyl transferase (GGT) alkaline phosphatase (ALP) bilirubin (total and direct) lactate dehydrogenase (LDH) total protein albumin	
	creatine kinase (CK) sodium chloride potassium creatinine blood urea nitrogen (BUN) fasting blood glucose	
Urinalysis	specific gravity, pH, glucose, protein, blood, ketones, bilirubin, urobilinogen, nitrite, leukocyte esterase by dipstick microscopic examination (if blood or protein is abnormal)	
Complement panel	Bb, C3a, C5a	
Immunogenicity	Antidrug antibodies	
Laboratory tests for admission to clinic	SARS-CoV-2 (local laboratory testing) Breath alcohol test (local laboratory testing) Urine drug screen (to include at minimum: amphetamines, barbiturates, cannabis, cocaine, opiates, and benzodiazepines)	
Pregnancy testing	Highly sensitive urine hCG pregnancy test (in female participants). Any positive urine pregnancy test will be confirmed with a serum pregnancy test (local laboratory testing)	
Other tests performed at Screening	Follicle-stimulating hormone (as needed to confirm menopausal status) Viral serology (human immunodeficiency virus antibody, hepatitis B surface antigen, and hepatitis C virus antibody) Hemoglobin A1c Urine drug screen (to include at minimum: amphetamines, barbiturates, cocaine, opiates, and benzodiazepines)	

10.3. Adverse Events: Definitions and Procedures for Recording, Evaluating, Follow-up, and Reporting

10.3.1. Definition of Adverse Event

An AE is any untoward medical occurrence in a patient or clinical study participant, temporally associated with the use of study intervention, whether or not considered related to the study intervention. An AE can therefore be any unfavorable and unintended sign (including an abnormal laboratory finding), symptom, or disease (new or exacerbated) temporally associated with the use of study intervention.

Events Meeting the AE Definition

- Any abnormal laboratory test results (hematology, clinical chemistry, or urinalysis) or other safety assessments (e.g., ECG, radiological scans, vital signs measurements), including those that worsen from baseline, considered clinically significant in the medical and scientific judgment of the Investigator.
- Exacerbation of a chronic or intermittent pre-existing condition, including either an increase in frequency and/or intensity of the condition.
- New condition detected or diagnosed after study intervention administration, even though it may have been present before the start of the study.
- Signs, symptoms, or the clinical sequelae of a suspected drug-drug interaction.
- Signs, symptoms, or the clinical sequelae of a suspected overdose of either study intervention or a concomitant medication. Overdose per se will not be reported as an AE/SAE unless it is an intentional overdose taken with possible suicidal/self-harming intent. Such overdoses should be reported regardless of sequelae.

Events NOT Meeting the AE Definition

- During the conduct of EIAs, participants will be questioned by site staff to assess the 6 symptoms (flushing, headache, lightheadedness, palpitations, nausea, and vomiting) associated with increased blood acetaldehyde levels. These symptoms solicited via active questioning do not meet the AE definition.
- Medical or surgical procedure (e.g., endoscopy, appendectomy): the condition that leads to the procedure is the AE.
- Situations in which an untoward medical occurrence did not occur (social and/or convenience admission to a hospital).
- Anticipated day-to-day fluctuations of pre-existing disease(s) or condition(s) present or detected at the start of the study that do not worsen.

10.3.2. Definition of Serious Adverse Event

If an event is not an AE per definition above, then it cannot be an SAE even if serious conditions are met.

An SAE is defined as any untoward medical occurrence that, at any dose:

- **Results in death**
- **Is life-threatening**

The term ‘life-threatening’ in the definition of ‘serious’ refers to an event in which the participant was at risk of death at the time of the event. It does not refer to an event that hypothetically might have caused death if it were more severe.

- **Requires inpatient hospitalization or prolongation of existing hospitalization**

In general, hospitalization signifies that the participant has been detained (usually involving at least an overnight stay) at the hospital or emergency ward for observation and/or treatment that would not have been appropriate in the physician’s office or outpatient setting.

Complications that occur during hospitalization are AEs. If a complication prolongs hospitalization or fulfills any other serious criteria, the event is serious. When in doubt as to whether “hospitalization” occurred or was necessary, the AE should be considered serious.

Hospitalization for elective treatment of a pre-existing condition that did not worsen from baseline is not considered an AE. Pre-planned hospitalizations scheduled prior to signing the ICF, for an elective medical/surgical procedure do not meet this criterion.

- **Results in persistent disability/incapacity**

The term disability means a substantial disruption of a person’s ability to conduct normal life functions.

This definition is not intended to include experiences of relatively minor medical significance such as uncomplicated headache, nausea, vomiting, diarrhea, influenza, and accidental trauma (e.g., sprained ankle), which may interfere with or prevent everyday life functions but do not constitute a substantial disruption.

- **Is a congenital anomaly/birth defect**
- **Other situations:**

Medical or scientific judgment should be exercised in deciding whether SAE reporting is appropriate in other situations, such as important medical events that may not be immediately life-threatening or result in death or hospitalization but may jeopardize the participant or may require medical or surgical intervention to prevent one of the other outcomes listed in the above definition. These events should usually be considered serious.

Examples of such events include invasive or malignant cancers, intensive treatment in an emergency room or at home for allergic bronchospasm, blood dyscrasias or convulsions that do not result in hospitalization, or development of drug dependency or drug abuse.

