^a “Time 0” is immediately before the first sip of ethanol is consumed. All Time 0 assessments must be performed prior to initiation of alcohol intake.^b Participants will arrive at the site after a minimum 3-hour fast, then will be provided a standardized meal before receiving the first drink. Participants will be given 30 minutes to consume the meal.^c Catheter placement may be performed earlier in the day if preferred, but participants must be given at least a 20-minute rest period following placement of the venous access catheter prior to recording pre-dose vital signs and ECG. For EIAs conducted prior to a dosing day, the venous catheter will be left in place for PK sample collections.^d If multiple assessments are due at the same timepoint, the order of assessments should be ECG, vitals, blood draw, then any other assessments. The 60-minute symptom assessment should be conducted before the start of the 4th drink.^e To include pulse rate and blood pressure.^f Blood samples will be collected via venous access device. To include acetaldehyde, acetate, and ethanol.^g Participants will be questioned by site staff to assess the 6 symptoms (flushing, headache, lightheadedness, palpitations, nausea, and vomiting) associated with increased blood acetaldehyde levels.^h Ethanol will be consumed in 4 aliquots over an 80-minute period (20 minutes for each aliquot). Time windows do not apply to ethanol consumption. The ethanol will be mixed in a liquid that has no other alcohol, no caffeine, and is low in sugar. The dose of ethanol will be 0.8 g/kg (to a maximum of 56 g) for men and 0.68 g/kg (to a maximum of 48 g) for women. See [Section 8.6.1.3](#) of the protocol for ethanol administration stopping rules.ⁱ AEs associated with administration of ethanol will include events spontaneously reported by participants beginning with the first sip of ethanol (symptoms elicited under direct questioning [footnote g] are not considered AEs).

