7.3. Individual Participant Stopping Rules

7.3.1. Serious Adverse Event

If a participant experiences an SAE ([Section 10.3.2](#)), unless it is clearly the result of a non-study-related event, further dosing of the participant will be paused while the SRC reviews the event. Based on this review, a decision will be made as to whether the participant may continue to receive doses of study intervention. In participants who have completed dosing, continued follow-up with protocol-specified assessments, including subsequent EIAs, will be pursued if the participant is willing and the PI determines it is safe to do so. Additional EIAs will not be performed if, in the clinical judgment of the PI and/or SRC, the SAE could be related to study intervention and that repeat EIAs pose a recurrent risk to the participant, or if the participant declines these additional assessments. Participants will continue to be followed for other study procedures as detailed in the SoA.

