8.3.1. Time Period and Frequency for Collecting Adverse Event Information

All AEs and SAEs will be collected from the time the ICF is signed through the last follow-up visit at the time points specified in the SoAs ([Section 1.3](#)).

All SAEs will be recorded and reported to the Sponsor or designee within 24 hours, as indicated in [Section 10.3.5](#). The Investigator will submit any updated SAE data to the Sponsor within 24 hours of it being available.

Investigators are not obligated to actively seek AE or SAE after conclusion of study participation. However, if the Investigator learns of any SAE, including a death, at any time after a participant has been discharged from the study, and he/she considers the event to be reasonably related to the study intervention or study participation, the Investigator must promptly notify the Sponsor.

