8.6.1. Ethanol Interaction Assessments

Serial EIAs will be performed to assess the indirect PD effects of ALDH2 reduction (acetaldehyde increase). EIAs will be conducted in accordance with the SoA in [Section 1.3](#). Should an EIA be missed, due to COVID-19 or other circumstances, the missed EIA may be conducted at an unscheduled visit at the discretion of the Investigator and the Sponsor.

Participants will be required to be fasted for at least 3 hours prior to administration of a standardized meal and must have a negative breath alcohol test on the day of the study visit prior to the EIA. Prior to each EIA, venous catheters will be placed at least 20 minutes before the first EIA vital signs are assessed at time 0. For EIAs conducted prior to a dosing day, the venous catheter will be left in place for PK sample collections.

Participants will consume a fixed dose of ethanol mixed in a liquid that has no additional alcohol, no caffeine, and is low in sugar. The ethanol dose will be 0.8 g/kg (to a maximum of 56 g) for male participants and 0.68 g/kg (to a maximum of 48 g) for female participants. Ethanol will be consumed in 4 equal aliquots over an 80-minute period (20 minutes for each

aliquot). During the EIA, participants will receive nothing by mouth (remain NPO) except water ad libitum. Assessments will be made over an estimated 4-hour period, as detailed in [Table 3](#).

Participants will remain in the Phase 1 unit for over-night observation. The Investigator will not discharge any participant experiencing ongoing effects of ethanol administration and will not do so until it is deemed medically safe to do so.

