8.6.1.2. EIA Physiologic Signs and Symptoms

EIA assessments will include the direct questioning of participants as to the presence of ethanol reaction symptoms (flushing, headache, lightheadedness, palpitations, nausea, and vomiting) at the times indicated in [Table 3](#). Note: the presence of these ethanol reaction symptoms will not be considered AEs.

A composite 6-symptom score for each participant during each EIA will be determined as follows:

- At each of the timepoints during the EIA, each symptom will be given a numeric score of 0 (not present) to 3 (present and severe), with the exception of vomiting, which will be given a score of 3.
- The composite symptom score for each of the EIA timepoints will be the summed value for each of the 6 symptoms at that timepoint (range 0 – 18).
- The Peak score for a given day's EIA will be the participant's highest post-alcohol ingestion timepoint score minus the participant's pre-alcohol score.

Vital signs (BP and heart rate) and standard 12-lead ECGs will be recorded at the times indicated in [Table 3](#).

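### Protocol 10.3.1 and 10.3.2 together bar a serious solicited EIA symptom from being an SAE; separately, SAP 4.13.3 drops EOS from the laboratory shift tables

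*Protocol*

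**What the plan says.** **(a) Solicited EIA symptoms.** During each EIA, site staff ask about flushing, headache, lightheadedness, palpitations, nausea and vomiting.

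- Protocol 10.3.1, on events that are not AEs: "These symptoms solicited via active questioning do not meet the AE definition."
- Protocol 8.6.1.2, on the same six: "the presence of these ethanol reaction symptoms will not be considered AEs."
- Protocol 1.3, Table 3 footnote i, keeps volunteered events in: "AEs associated with administration of ethanol will include events spontaneously reported by participants beginning with the first sip of ethanol". It leaves out symptoms found by direct questioning.
- Protocol 10.3.2 opens with the rule: "If an event is not an AE per definition above, then it cannot be an SAE even if serious conditions are met." Lower down, in the text on hospitalization, it says: "Complications that occur during hospitalization are AEs. If a complication prolongs hospitalization or fulfills any other serious criteria, the event is serious."
- Protocol 8.3.1 attaches a deadline to SAE status: "All SAEs will be recorded and reported to the Sponsor or designee within 24 hours". Section 9.4.2 makes the incidence and severity of AEs and SAEs a primary endpoint.

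**(b) Laboratory shift tables.** Protocol 9.4.2 asks for laboratory shifts from baseline to abnormal post-baseline values by treatment group and excepts no visit. SAP 4.13.3 says the hematology and biochemistry shift tables will run from baseline to every post-dose time point. It then says that Screening and EOS measurements stay out of those tables. SAP 4.21, on changes to the planned analysis, reads Not Applicable.

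**The concern.** (a) Taking expected, prompted symptoms out of the AE tables is reasonable, because they feed the composite score that Protocol 9.4.3 names as the principal secondary endpoint. The difficulty is that the exclusion has no upper limit. A prompted symptom that became life-threatening or led to hospital admission is treated like mild flushing. If it had been recorded only through the questionnaire, the text would keep it out of three places:

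- SAE labelling, and with it the SAE dosing pause in 7.3.1;
- the 24-hour report to the sponsor;
- the SAE count in a primary endpoint.

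AE status would also depend on whether the participant spoke first or was asked first.

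(b) The shift table is the only low/normal/high cross-tabulation that the SAP describes for hematology and biochemistry. Apart from liver chemistry, SAP 4.13.3 declines to tabulate clinically significant values separately. Leaving EOS out removes the last scheduled on-study category shift from a primary safety endpoint. Protocol 4.2 justifies the 24-week follow-up by saying that effects may take months to appear.

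**Working it through.** The plan gives no figure to reproduce here. It has no sample-size calculation (Protocol 9.2) and is descriptive (9.1). The check is a reading of the text, plus some day arithmetic for (b).

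**(a) Do 10.3.1 and 10.3.2 conflict, and what follows if not?**

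1. Premise from 10.3.1, repeated in 8.6.1.2 and Table 3 footnote i: a solicited EIA symptom is not an AE. None of the three places makes an exception for seriousness.
2. Premise from the first sentence of 10.3.2: an event that is not an AE is not an SAE, whatever serious conditions it meets.
3. Conclusion: a solicited EIA symptom is not an SAE, however serious. The two sections give one answer.
4. The line on complications during hospitalization does not reverse this. It explains one seriousness criterion and sits below the sentence that makes AE status a precondition.
5. Section 7.3.1 foresees cases where "the SAE could be related to study intervention and that repeat EIAs pose a recurrent risk to the participant". That is compatible with step 3, because a volunteered EIA event is an AE and can be an SAE. It does show that the protocol expects SAEs connected with EIAs, so excluding the prompted ones is probably unintended (my inference).

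**What stays inside AE capture:**

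- events volunteered from the first sip onward (Table 3 footnote i);
- the underlying diagnosis, which 10.3.4.1 prefers to individual symptoms where one can be made;
- clinically significant vital-sign or ECG findings (10.3.1), both of which are measured in each EIA;
- events outside the six symptoms, such as syncope.

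What is left is a serious reaction that appears only as an answer to the questionnaire.

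**(b) Scope and timing of the shift tables.**

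- Protocol 9.4.2 scope: all post-baseline values. SAP 4.13.3 scope: every post-dose time point, less EOS. The SAP scope is narrower than the protocol's and contradicts the SAP's own description.
- EOS is post-baseline, because baseline is the last value before dosing (Protocol 9.4.1; SAP 4.2.4). I read the schedule tables as placing hematology and chemistry at EOS; their columns are damaged in the text I have.
- Last dose is Day 57. EOS is Day 168 or 169, depending on which day of the visit is counted. Days after last dose: 168 − 57 = 111, or 169 − 57 = 112.
- The SAP 4.2.7 dosing period ends 58 days after the last dose: 57 + 58 = Day 115. EOS falls 168 − 115 = 53 or 169 − 115 = 54 days later.

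EOS is therefore outside the SAP's dosing period. However, the SAP neither restricts the shift tables to that period nor gives it as the reason for the exclusion.

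**The case against.** **On (a).** A reader might infer that 10.3.1 and 10.3.2 contradict each other, or that 10.3.2 contradicts itself through the hospitalization line and the EIA arrangement "Participants will remain in the Phase 1 unit for over-night observation". The documents do not support that. The opening sentence of 10.3.2 governs what follows it. The section also describes hospitalization as detention for care that would not suit an outpatient setting, which a routine stay planned for every participant at every EIA does not readily fit. A reader might also point to the 10.3.1 entry on suspected drug-drug interactions as a way back in for an alcohol reaction. The exclusion of the six solicited symptoms is the more specific text, so I do not rely on that entry.

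The best counter-argument is that the gap is almost empty in practice. Besides the capture routes above:

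- 7.3.4 stops further dosing of a participant with a significant negative reaction;
- Table 5 interrupts all dosing and enrollment after one significant or severe symptom, until the SRC has reviewed it;
- 7.4 has a three-participant rule;
- Section 8 asks that urgent safety concerns go to the sponsor immediately;
- the Sponsor Medical Monitor sits on the SRC (10.1.5.1).

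Most of this stands. It defeats any claim that clinical oversight is lost. It does not supply the SAE label, the formal 24-hour report or the entry in the primary count.

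**On (b).** Protocol 9.4 is introduced as a summary, with detail left to the SAP, and 9.4.2 names no visits. So this is an undeclared narrowing of general wording and does not breach a visit list. A reader might infer that EOS laboratory data go unreported. They do not: EOS is not excluded from the time-point summaries, change-from-baseline summaries or listings, and clinically significant values become AEs. The SAP's contradiction with its own text remains.

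**Conclusion.** Both points hold, and both are minor.

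(a) This is a reporting gap with no contradiction behind it. It affects only a serious reaction captured solely by questioning, and it costs a label, a report and a count. I do not estimate how often that would happen, because the documents give no rate. The only human experience they cite is no SAEs among 24 single-dose DCR-AUD participants in the first-in-human study (Protocol 2.2), which gave half the ethanol used here (4.2). That suggests few events but sets no limit for repeat dosing at double the ethanol. The conclusion assumes that sites follow the text literally; a cautious investigator might report the event anyway.

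(b) SAP 4.13.3 is inconsistent with itself and narrower than Protocol 9.4.2, and SAP 4.21 does not declare the difference. The loss is one visit in one type of table, in a descriptive trial of 16 participants. The wording looks like template carry-over. The next sentence speaks of dosing in each period, although this is a parallel-group trial, and SAP 4.13.5 repeats the exclusion for ECG, where no shift table is described. That origin is an inference.

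**What to change.** **(a)** Add one sentence to Protocol 10.3.1, 8.6.1.2 and Table 3 footnote i: a solicited EIA symptom that meets any seriousness criterion in 10.3.2 is recorded and reported as an AE/SAE, labelled EIA-associated, and is still scored for PD; the planned overnight stay is not itself a seriousness criterion. Leave 7.4 as it is. The cost is that a few expected alcohol reactions may enter the AE/SAE tables, where the label identifies them. They would also count under the existing grade rules in 7.4, which still need an SRC recommendation before dosing stops.

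**(b)** In SAP 4.13.3, delete the EOS exclusion so that EOS values enter the hematology and biochemistry shift tables, and say how early-termination values are handled, since they share the EOS column. If an on-treatment table is really intended, say so by reference to SAP 4.2.7 and record the difference from Protocol 9.4.2 in SAP 4.21. A worst-post-baseline row would be useful but is optional; neither document promises one. The cost is a wording change, for which SAP Section 1 already provides a modification form. No new data are needed.
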